CLINICAL PROTOCOL

Transcranial Focused Ultrasound Neuromodulation for Post-Stroke Motor Dysfunction

Sponsoring Institution: Taizhou People's Hospital

Principal Investigator / Department: [name] / Department of Rehabilitation Medicine

Study Period: March 2026 – March 2028

Version: 2.0

Version Date: April 27, 2026

Protocol Synopsis

Project Title	Clinical Protocol for Transcranial Focused Ultrasound Neuromodulation in Post-Stroke Motor Dysfunction
Study Objectives	This study aims to evaluate how transcranial focused ultrasound (tFUS) technology promotes the remodeling of damaged neural networks and functional recovery by activating or inhibiting neural activity in specific brain regions, integrating electroencephalography (EEG) and magnetic resonance imaging (MRI) signal analyses. The primary goals are to improve motor ability and cognitive function, reduce long-term disability, and enhance quality of life. Additionally, this study seeks to optimize stimulation parameters to achieve maximal rehabilitative outcomes and to elucidate the potential mechanisms underlying neuroprotection and functional reconstruction following stroke.
Study Design	This study is a randomized, controlled, single-center trial.
Sample Size	60 participants
Participant Selection	Inclusion Criteria: (1) Patients with a confirmed imaging diagnosis of first-ever ischemic stroke; (2) Unilateral limb motor involvement; (3) Modified Ashworth Scale (MAS) grade ≤ 3 for the upper extremity, Brunnstrom stage II–V, and upper extremity Fugl-Meyer Assessment (FMA-UE) score between 15 and 60 (inclusive); (4) Age 18–75 years, onset within 21 days to 6 months, in the subacute or recovery phase; (5) Stable vital signs, no consciousness impairment, informed consent provided, ability to cooperate with clinical assessments, and approval obtained from the institutional ethics committee. Exclusion Criteria: (1) Contraindications to MRI; (2) Infarction involving the thalamus; (3) Risk of intracranial hemorrhage; (4) Presence of intracranial metallic foreign bodies, cardiac pacemakers, or cochlear implants; (5) Unstable medical condition, severe cognitive impairment or psychiatric disorders rendering the patient unable to comprehend the study or cooperate with assessments; (6) Conditions affecting limb motor function, including fractures, joint contractures, or severe limb spasticity; (7) Current use of medications that alter cortical excitability.
Treatment Protocol	Neuromodulation Group: Multimodal neuromodulation targeting specific neural regions in addition to conventional therapy. Control Group: Sham stimulation in addition to conventional therapy.
Efficacy Assessment	Primary Outcome Measures: Fugl-Meyer Assessment score; neuroimaging data (cranial CT/MRI); EEG measurements of resting-state and task-state spectral power and functional connectivity; laboratory parameters (complete blood count, CRP, IL-6, S100 β , BDNF). Secondary Outcome Measures: Brunnstrom staging, Modified Ashworth Scale grading, muscle strength, and patient comfort assessment. Safety Assessment Indicators: Complete blood count, blood biochemistry, coagulation function.
Statistical Methods	Key outcome measures will be compared between the neuromodulation group and the control group before and after intervention using independent samples t-tests (two groups) or analysis of variance (multiple groups) to detect statistically significant intergroup differences. Non-parametric tests will be applied to data not conforming to a normal distribution.
Study Duration	March 2026 – March 2028

1. Background and Rationale

According to the World Health Organization (WHO), stroke is the second leading cause of death globally [1]. Approximately 15 million individuals worldwide experience a stroke annually, ranking second only to heart disease, and stroke remains one of the most prevalent causes of long-term disability. Ischemic stroke (IS) constitutes the most common subtype, accounting for approximately 85% of all stroke cases [2]. Among all stroke survivors, over 60% experience varying degrees of functional impairment within three months following the event. The American Stroke Association (ASA) has reported [3] that approximately one-third of stroke patients develop severe speech impairment post-stroke, while one in two patients sustains some degree of hand function loss. Stroke patients frequently contend with chronic functional deficits, including motor difficulties, speech impairment, and cognitive dysfunction, all of which profoundly compromise quality of life. These patients typically require prolonged rehabilitation and nursing care, imposing substantial financial burden on families and exerting considerable pressure on healthcare systems.

Conventional pharmacological and rehabilitative interventions for stroke may yield limited efficacy, particularly in patients with severe cerebral injury. Pharmacological therapies such as anticoagulants carry inherent hemorrhagic risks, while the effectiveness of traditional rehabilitation approaches may be negligible in patients with severe functional deficits, often requiring protracted recovery periods. In recent years, neuromodulation technologies have demonstrated significant potential in the investigation and treatment of neurological disorders including stroke [4]. Given that ischemic stroke involves complex neural network dysfunction, neuromodulation technologies, as an emerging therapeutic modality, offer novel avenues for overcoming the limitations of conventional approaches. By activating or inhibiting neural activity in specific brain regions, neuromodulation may promote neural repair, restructure functional networks, and enhance motor and cognitive capabilities. Evidence indicates that deep brain stimulation (DBS) [5] and transcranial magnetic stimulation (TMS) [6] can facilitate the restoration of post-stroke functional deficits by augmenting inter-regional connectivity or reactivating compromised neural pathways.

Nevertheless, prevailing mainstream neuromodulation modalities continue to exhibit substantial limitations that preclude the adequate fulfillment of clinical demands in ischemic stroke management. Specifically, deep brain stimulation (DBS), while demonstrating reliable modulatory efficacy, constitutes an invasive procedure requiring surgical implantation of electrodes, entailing risks of infection, hemorrhage, and other surgery-related complications, as well as the potential for irreversible tissue damage. Moreover, the prohibitive surgical costs and complex postoperative maintenance restrict its applicability in patients with mild symptoms or advanced age. Transcranial magnetic stimulation (TMS), although noninvasive, suffers from limited spatial resolution, rendering it incapable of precisely targeting specific neural pathways in deep brain structures. This limitation predisposes the technique to nonspecific stimulation of surrounding normal brain tissue, resulting in variable modulatory outcomes. Furthermore, its constrained stimulation depth yields suboptimal therapeutic effects in ischemic stroke patients with deeply situated lesions.

In this context, transcranial focused ultrasound (tFUS), as an emerging noninvasive neuromodulation technology, has exhibited distinctive technical advantages [7], presenting novel possibilities for breakthroughs in ischemic stroke treatment [8]. Compared with conventional neuromodulation modalities, tFUS possesses exceptionally high spatial

resolution, enabling precise focusing on lesion sites within deep brain regions and targeted modulation of specific neural networks, thereby effectively circumventing interference with surrounding normal brain tissue. Simultaneously, tFUS requires no craniotomy, is entirely noninvasive, significantly reduces the risk of complications, improves patient treatment compliance, and offers adjustable stimulation depth applicable to ischemic stroke patients with varying lesion depths. Additionally, tFUS can modulate blood-brain barrier permeability [9], facilitating the delivery of neurorepair-related pharmacological agents to lesion sites and achieving synergistic effects between neuromodulation and pharmacotherapy.

Therefore, conducting research on tFUS neuromodulation in ischemic stroke patients is of considerable importance. Such research not only addresses the technological shortcomings of existing neuromodulation therapies by providing safer, more precise, and more effective treatment strategies for ischemic stroke patients, but also further elucidates the intrinsic mechanisms of neural repair following ischemic stroke, thereby advancing both theoretical innovation and clinical translation in the field of stroke neuromodulation [10].

2. Study Objectives

2.1 Primary Objective: This study aims to evaluate how tFUS technology promotes the remodeling of damaged neural networks and functional recovery by activating or inhibiting neural activity in specific brain regions, integrating EEG and MRI signal analyses. The primary goals are to improve motor ability and cognitive function, reduce long-term disability, and enhance quality of life. Additionally, this study seeks to optimize stimulation parameters to achieve maximal rehabilitative outcomes and to elucidate the potential mechanisms underlying neuroprotection and functional reconstruction following stroke.

2.2 Secondary Objective: To explore novel therapeutic protocols for upper limb rehabilitation following stroke.

3. Study Overview

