3.2 Sample Size

Participants will be recruited from inpatients of the Department of Rehabilitation Medicine. Based on preliminary literature review and the current inpatient volume of our department, the provisional sample size is set at $n = 60$, with 30 participants allocated to each group.

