3.4 Participant Selection

Inclusion Criteria: (1) Patients with a confirmed imaging diagnosis of first-ever ischemic stroke; (2) Unilateral limb motor involvement; (3) Modified Ashworth Scale (MAS) grade ≤ 3 for the upper extremity, Brunnstrom stage II–V, and upper extremity Fugl-Meyer Assessment (FMA-UE) score between 15 and 60 (inclusive); (4) Age 18–75 years, onset within 21 days

to 6 months, in the subacute or recovery phase; (5) Stable vital signs, no consciousness impairment, informed consent provided, ability to cooperate with clinical assessments, and approval obtained from the institutional ethics committee.

Exclusion Criteria: (1) Contraindications to MRI; (2) Infarction involving the thalamus; (3) Risk of intracranial hemorrhage; (4) Presence of intracranial metallic foreign bodies, cardiac pacemakers, or cochlear implants; (5) Unstable medical condition, severe cognitive impairment or psychiatric disorders rendering the patient unable to comprehend the study or cooperate with assessments; (6) Conditions affecting limb motor function, including fractures, joint contractures, or severe limb spasticity; (7) Current use of medications that alter cortical excitability.

Withdrawal Criteria: (1) Health risks: Occurrence of serious health events such as acute cardiovascular events or other severe illnesses; (2) Non-compliance: Failure to adhere to the treatment protocol or follow-up requirements, compromising data reliability; (3) Personal reasons: Voluntary withdrawal from the study due to personal circumstances; (4) Severe adverse reactions: Occurrence of unmanageable treatment-related discomfort, such as extreme pain or allergic reactions.

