3.5.5 Group Allocation

A total of 60 patients with hemiplegic upper limb dysfunction during the recovery phase of stroke, undergoing inpatient rehabilitation at the Department of Rehabilitation Medicine, Taizhou People's Hospital, will be randomly allocated into a neuromodulation group and a

control group (n = 30 per group) using a random number table. All participants in both groups will receive conventional pharmacological therapy (including antiplatelet aggregation agents, neurotrophic agents, circulatory improvement agents, plaque stabilizers, antihyperglycemic/antihypertensive agents, and supportive therapy) and standard rehabilitation interventions (physical therapy and occupational therapy). The neuromodulation group will receive one week of transcranial focused ultrasound stimulation in addition to conventional treatment. The control group will undergo the same assessment and procedural steps as the experimental group but will receive sham stimulation.

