3.8 Efficacy Assessment

Primary Outcome Measures: Post-treatment (immediate and 2-week follow-up) upper extremity Fugl-Meyer Assessment score, Brunnstrom staging, and Modified Ashworth Scale grading; neuroimaging data (analysis of ALFF, fALFF, ReHo, FC, and FA indices using functional MRI and diffusion tensor imaging); EEG measurements of resting-state and task-state spectral power and functional connectivity.

Secondary Outcome Measures: Blood biochemistry, complete blood count, C-reactive protein (CRP), interleukin-6 (IL-6), S100 β protein, and brain-derived neurotrophic factor (BDNF).

4. Risks and Benefits

4.1 Potential Risks and Mitigation Measures: Abnormal reactions to ultrasound stimulation and potential induction of seizures. Adverse symptoms such as dizziness and headache will be promptly managed. Short-term administration of analgesic agents and antiepileptic medications will be employed as indicated.

4.2 Potential Benefits and Compensation for Participants:

Direct Benefits: Promotion of hemiplegic upper limb functional recovery and enhancement of activities of daily living capacity.

Societal Benefits: It is anticipated that information obtained from this study may benefit the participant or future patients with similar conditions.

5. Adverse Event Monitoring

5.1 Adverse Events (AEs): An adverse event is defined as any unfavorable medical occurrence, unanticipated illness or injury, or unexpected clinical sign (including abnormal laboratory findings) in a participant or other individual, regardless of whether it is considered related to the study intervention or treatment strategy under investigation.

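### Time since onset may range from 21 days to 6 months at entry, but neither the allocation nor the fixed unadjusted t-test uses it, which may cost precision on FMA-UE

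*Protocol*

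**What the plan says.** **Entry.** The Synopsis (Participant Selection) and section 3.4 both accept "onset within 21 days to 6 months, in the subacute or recovery phase". Neither phase is defined in days.

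**Phase at allocation.** Section 3.5.5 describes those to be randomised as "60 patients with hemiplegic upper limb dysfunction during the recovery phase of stroke" and does not mention the subacute phase.

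**Allocation.** Section 3.5.5 allocates "using a random number table" and names no stratification factor. Section 3.2 sets the provisional total at 60, "with 30 participants allocated to each group".

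**Comparison.** The Synopsis (Statistical Methods) says key outcomes will be "compared between the neuromodulation group and the control group before and after intervention using independent samples t-tests", with analysis of variance for more than two groups and non-parametric tests for non-normal data. No covariate is named.

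**Timing.** Section 3.6 describes a one-week programme of five sessions, with post-test MRI within two days of the last. Section 3.8 lists as a primary outcome "Post-treatment (immediate and 2-week follow-up) upper extremity Fugl-Meyer Assessment score". The FMA-UE readings therefore fall about one and about three weeks from baseline; the second figure is derived (1 + 2 weeks), not stated.

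**Data.** Section 3.5.4 collects the history of the present illness but does not list onset date as a field.

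**The concern.** From day 21 to about day 183 is a range of 183 / 21 = 8.7-fold in time since stroke. If patients near the lower limit are still improving on their own and patients near the upper limit are not, a short-interval change in FMA-UE depends partly on when the patient entered. The sham arm removes the average of that natural gain but not its spread between patients. The spread goes into the error term of an unadjusted t-test, and with 30 per arm the arms can differ in mean time since onset by chance. A value that every eligibility check requires could take out much of this noise, but the stated comparison leaves it unused.

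The difference in phase wording bears on the same point. If the two phases are meant to be distinct, section 3.5.5 describes a narrower range of onset times than section 3.4 admits.

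**Working it through.** **Nothing to reproduce.** Section 3.2 gives no effect size, SD, significance level or power, so the total of 60 cannot be re-derived. For orientation, at an assumed two-sided 5% level, 30 per arm gives 80% power for a standardised difference of (1.96 + 0.84) × √(2/30) = 0.72, and 49% power at 0.5 (normal approximation).

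**Inputs from the protocol.** Onset 21 days to 6 months (3 to 26 weeks); 30 per arm; FMA-UE read at about one and about three weeks.

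**Assumed inputs, none in the protocol.** Entry uniform over 3-26 weeks; natural three-week gain g(t) = G × 2^(−(t−3)/6) for entry at week t, with G = 4, 6 or 10 points at week 3 and a six-week half-life; residual SD of change s = 3, 5 or 8 points.

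**Step 1, chance imbalance in onset.** SD = 23/√12 = 6.64 weeks. SE of the difference in arm means = 6.64 × √(2/30) = 1.71 weeks; 95% range ±1.96 × 1.71 = ±3.36 weeks. In days (uniform over 21-183) the SE is 12.1, and the chance of an imbalance above 14 days is about 25%. It is about 11% if entry is skewed towards early patients.

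**Step 2, three-week change.** Under the uniform distribution the SD of g is 0.2545 × G. The shift in the arm difference from imbalance alone is ±1.96 × SD(g) × √(2/30). The share of variance explained is R² = SD(g)² / (SD(g)² + s²).

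| G | SD of g | 95% shift | R², s = 3 | R², s = 5 | R², s = 8 |
|---|---|---|---|---|---|
| 4 | 1.02 | ±0.52 | 10% | 4% | 2% |
| 6 | 1.53 | ±0.77 | 21% | 9% | 4% |
| 10 | 2.55 | ±1.29 | 42% | 21% | 9% |

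**Step 3, immediate readout.** On the same curve the one-week gain is (1 − 2^(−1/6)) / (1 − 2^(−3/6)) = 0.109 / 0.293 = 37% of the three-week gain. The shifts fall to ±0.2, ±0.3 and ±0.5 points. R² at s = 3 to 5 runs from 0.6% (G = 4, s = 5) to 9% (G = 10, s = 3), so about 1-9%.

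**Step 4, what adjustment buys at three weeks.** The 95% half-width is 1.96 × SD × √(2/30). The unadjusted SD is √(SD(g)² + s²); if onset time is fully accounted for, it is s.

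| G | s | Unadjusted | Adjusted |
|---|---|---|---|
| 4 | 3 | 1.60 | 1.52 |
| 4 | 5 | 2.58 | 2.53 |
| 10 | 3 | 1.99 | 1.52 |
| 10 | 5 | 2.84 | 2.53 |

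In power terms, at a standardised difference of 0.5, R² = 0.05 lifts power from 49% to 51% and R² = 0.20 lifts it to 58%. The latter is equivalent to 30 / (1 − 0.20) = 37.5 per arm.

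**Step 5, form of the covariate.** On this curve log time since onset captures 99% of the onset-related variance and linear time 90%.

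**Step 6, a second curve.** With an exponential curve (20-40 points, time constant 4-10 weeks, uniform or early-skewed entry) and other SD of 4-8 points, time since onset explains 1-35% of variance. For an assumed 4-point effect and other SD of 6, power is 64-72% unadjusted against 73% with onset time fully accounted for.

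**The case against.** **The premise is not in the protocol.** It gives no recovery rate, FMA-UE SD or decay curve. This stands: the loss is conditional on the assumed curves, and at the low end it is negligible.

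**Randomisation already covers imbalance.** A reader might infer that an early-heavy active arm would create a hidden bias. The documents do not support that. Under random allocation, chance imbalance in onset time is part of the t-test's standard error and type I error. The cost is a wider interval. Nor does anything prevent onset time from appearing in a baseline table.

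**The three-week window does not fit every outcome.** Post-test MRI and the last EEG-coupled session lie about one week from baseline, and FMA-UE also has an immediate reading. This stands, and step 3 allows for it. No effect on MRI or EEG can be sized.

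**Change scores are not specified.** The Synopsis does not say that the outcome is change. If raw post-treatment scores are compared, entry scores of 15-60 (uniform, SD 45/√12 = 13.0, assumed) dominate. Time since onset then explains only 0.6-3.7% of variance, as 1.02² / (1.02² + 169) and 2.55² / (2.55² + 169) show. This stands, and is a reason to adjust for baseline FMA-UE as well.

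**Covariates belong in a SAP.** Often so, and one may exist. But the Synopsis does not leave the method open: it names an unadjusted test, and a SAP that added a covariate would depart from that text. The allocation method and phase wording belong to the protocol itself.

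**The phase wording is not a contradiction.** A reader might infer that a patient at day 25 is eligible under section 3.4 but outside section 3.5.5. With neither phase defined in days, and the same numerical window in the Synopsis and section 3.4, that cannot be shown. It is an ambiguity to reconcile.

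**Conclusion.** The point holds as one of precision. The protocol admits a wide range of onset times, names no stratification on them, and fixes a comparison that ignores them. On the assumed curves, time since onset accounts for about 4-42% of the variance in three-week FMA-UE change at a residual SD of 3-5 points, about 2-9% at a residual SD of 8, and about 1-9% at the immediate readout (residual SD 3-5). The gain from adjustment thus runs from negligible to moderate, and the documents cannot narrow it further. The phase wording is a separate, minor inconsistency.

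**What to change.** 1. List days from stroke onset to randomisation as a baseline variable in section 3.5.4 and report it by arm.
2. In the Synopsis (Statistical Methods), replace the unadjusted t-test on FMA-UE with a pre-specified ANCOVA that includes log time since onset and baseline FMA-UE. The same onset covariate may be used for the MRI and EEG indices, though its benefit there is unknown.
3. Reconcile "in the subacute or recovery phase" in the Synopsis and section 3.4 with the wording of section 3.5.5, and define whichever terms are kept. Which population to enrol is a clinical decision and is not proposed here.

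The cost is a few lines of amendment and one degree of freedom per covariate. No extra patient or visit is needed, since onset time must already be established for eligibility. Section 8 schedules randomisation from June 2026, after this version's date of April 2026, so pre-specification looks feasible on the stated timeline.

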3.6 Neuromodulation Intervention

The transcranial focused ultrasound stimulation device employed in this study is the NeuroFUS DPX-500, equipped with a 4-element transducer array and the BrainSight neuronavigation system. Individualized modeling and target segmentation are performed using high-resolution structural MRI and CT images acquired at baseline. Target planning and neuronavigation are conducted based on intracranial acoustic field simulation. The total stimulation duration is 12 minutes, comprising 480 pulse trains with 0.5 seconds on and 1 second off, yielding a duty cycle of 20%. The intensity at the intracranial target site (after skull attenuation) is uniformly set at 8 W/cm².

Experiments will be conducted in a soundproofed, electromagnetically shielded room free from excessive illumination or reflective surfaces. The facility is equipped with provisions for prompt hair washing and EEG cap cleaning, and is situated within a 10-minute walk to the MRI suite.

The experimental protocol spans one week and comprises three principal phases: pre-test, neuromodulation, and post-test. The pre-test includes cranial MRI acquisition, clinical scale assessment, and EEG data collection. Neuromodulation sessions are administered once daily for a total of five sessions per week, with EEG recordings obtained before, during, and after each stimulation session. The post-test consists of cranial MRI acquisition identical to the pre-test protocol, conducted within two days of completion of all neuromodulation sessions.

The pre-test serves as a baseline measurement and primarily includes neuroimaging acquisition and resting-state/task-state EEG measurements. Neuroimaging acquisition encompasses cranial CT (the most recent CT obtained proximal to onset per admission protocol) and cranial MRI acquired using study-specific sequences, including T1-weighted, T2-weighted, resting-state functional MRI, and diffusion tensor imaging. Pre-test data are also utilized for individualized neuronavigation and acoustic field modeling simulation. This involves deep brain nuclei segmentation based on individual structural images, recording of target coordinates via the neuronavigation system, cranial acoustic parameter analysis using CT and structural images, planning of individualized neuromodulation incidence positions and parameter sequences by setting a uniform in situ target intensity, and concurrent safety testing and thermal simulation.

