Five neuromodulation sessions are administered in total. Sessions 2 and 5 involve simultaneous EEG-coupled ultrasound neuromodulation, while Sessions 1, 3, and 4 consist of ultrasound neuromodulation alone. During EEG-coupled sessions, EEG signals are acquired before, during, and after ultrasound stimulation; during standalone sessions, only ultrasound stimulation is delivered without EEG acquisition. Stimulation parameters are maintained at consistent control levels across participants. Based on each individual's

cranial acoustic parameters, the pre-attenuation stimulation intensity is back-calculated to ensure uniform in situ intensity at the target. The spatial-peak temporal-average intensity at the target is maintained below the diagnostic ultrasound safety threshold (720 mW/cm²). The ultrasound stimulation duration is 12 minutes using a 20% duty cycle pulse sequence.

The post-test cranial MRI protocol is identical to the pre-test and is performed within two days of completion of all neuromodulation sessions.

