5.2 Serious Adverse Events (SAEs): Serious adverse events are defined as events

occurring during the clinical trial that necessitate hospitalization, prolong existing hospitalization, result in disability, impair work capacity, are life-threatening or fatal, or cause congenital anomalies.

6. Ethical Considerations

6.1 The clinical study shall be conducted only after the trial protocol has been approved by the Ethics Committee prior to the commencement of the study. The investigator is required to promptly report all changes occurring in the course of the research to the Ethics Committee (including modifications to the protocol and/or informed consent form), and shall not implement such changes without prior approval from the Ethics Committee, unless the changes are necessary to eliminate an apparent and immediate risk to participants. In such circumstances, the Ethics Committee shall be notified.

6.2 Prior to enrollment of each participant, the investigator bears the responsibility of thoroughly informing the participant or their legal guardian of the study's objectives, procedures, potential risks, and information regarding alternative treatments, and of obtaining a signed written informed consent form. Participants shall be informed of their right to withdraw from the study at any time. Informed consent forms shall be retained as clinical research documentation for inspection. Throughout the study, the privacy of participants and the confidentiality of their data will be protected.

7. Data Confidentiality

Results obtained from this study may be published in medical journals; however, patient information shall be maintained in strict confidence in accordance with applicable legal requirements. Personal information of patients shall not be disclosed unless mandated by relevant laws and regulations. When necessary, governmental regulatory authorities, the institutional ethics committee, and their designated personnel may access patient records in accordance with applicable regulations.

8. Anticipated Timeline and Completion Date

The total duration of this project is two years, from March 2026 to March 2028. The planned schedule is as follows:

March 2026 – May 2026: Study preparation.

June 2026 – October 2026: Randomized group allocation of enrolled stroke patients, intervention implementation, and collection of relevant outcome measures.

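### Seizure is a named risk of stimulation, but the listed safety indicators are blood tests only and no reporting or review step is stated for a seizure or SAE

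*Protocol*

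**What the plan says.** - **Named risk.** Section 4.1 gives the risks as "Abnormal reactions to ultrasound stimulation and potential induction of seizures". Its response is treatment: "Short-term administration of analgesic agents and antiepileptic medications will be employed as indicated".
- **Safety measures.** The synopsis, in its Efficacy Assessment row, has "Safety Assessment Indicators: Complete blood count, blood biochemistry, coagulation function". Section 3.8 has no safety list; it places blood biochemistry and complete blood count among the secondary outcomes.
- **Adverse events.** Section 5 is headed as monitoring. Section 5.1 reads "An adverse event is defined as any unfavorable medical occurrence, unanticipated illness or injury, or unexpected clinical sign", whether or not the event is thought related. Section 5.2 defines SAEs as events "occurring during the clinical trial that necessitate hospitalization, prolong existing hospitalization, result in disability, impair work capacity, are life-threatening or fatal", or that cause congenital anomalies. Section 5 ends there.
- **Nearby provisions.** Section 3.4 allows withdrawal for serious health events (criterion 1) and for unmanageable treatment-related discomfort (criterion 4). Section 3.6 requires safety testing and thermal simulation during planning, and keeps the spatial-peak temporal-average intensity at the target below 720 mW/cm². Section 6.1 requires changes in the research to be reported to the Ethics Committee. Section 9 lists a Quality Control role without describing its duties.

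**The concern.** The protocol identifies one specific neurological harm and then lists safety measures that cannot show it. Blood counts, biochemistry and coagulation results could all be unremarkable in a trial in which seizures occurred. A safety summary built on the listed indicators would then read as clean.

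The second part is process. A seizure on the ward would be treated under section 4.1, but the protocol does not say who must be told, how soon, or who looks at events across participants. SAEs in general are in the same position: they are defined, and nothing is said about what follows. Reporting routes belong in the protocol, so a statistical analysis plan that is not shown would not normally supply them.

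At stake are the safety of participants who would otherwise continue stimulation after a seizure, and the trial's ability to say anything reliable about the risk it names.

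**Working it through.** There is no figure in the plan to reproduce. The check is a reading of every provision that might detect, report or review a seizure, followed by a small calculation for the optional pause rule.

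**1. Provisions set side by side**

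| Provision | What it does | Does it record, report or review a seizure? |
|---|---|---|
| Synopsis, safety indicators | Three groups of blood tests | No |
| 4.1 | Treats symptoms in the affected person | No |
| 5.1 | Defines adverse events broadly | Brings a seizure into scope; gives no route, deadline or reviewer |
| 5.2 | Defines SAEs | Same |
| 3.4, criteria 1 and 4 | Withdraws one participant; seizure not named | No |
| 3.6, safety testing, thermal simulation, 720 mW/cm² limit | Prevention | No |
| 3.6, EEG | Recorded around stimulation | Only in part; see step 2 |
| 6.1 | Reports changes in the research; permits an urgent change | Adverse events not named |
| 9, Quality Control | A role with no stated duties | No |

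**2. EEG as a possible detector**

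Section 3.6 first has EEG at every session ("with EEG recordings obtained before, during, and after each stimulation session"). It then limits EEG to sessions 2 and 5, and for the other three says "during standalone sessions, only ultrasound stimulation is delivered without EEG acquisition". On either reading EEG is listed as an efficacy outcome, and it does not cover the time between sessions or the two weeks to follow-up.

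**3. Would a seizure at least be an SAE?**

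Not necessarily. Participants are "undergoing inpatient rehabilitation at the Department of Rehabilitation Medicine", so a brief seizure treated on the ward might neither cause nor prolong a hospital stay. Little turns on this, because no reporting step is stated for SAEs either.

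**4. What 30 active participants can show**

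Input: 30 per group (section 3.2). If no seizure is seen in 30, the one-sided 95% upper limit on the rate is 1 − 0.05^(1/30) = 9.5%. Even that modest statement needs seizures to be recorded systematically.

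**5. Optional pause at the second affected active participant**

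The protocol gives no seizure rate, so p = 1% and 2% per active participant are assumptions.

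P(at least 2 of 30) = 1 − (1−p)^30 − 30p(1−p)^29

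- p = 1%: 1 − 0.7397 − 0.2242 = 0.0361, or 3.6%
- p = 2%: 1 − 0.5455 − 0.3340 = 0.1205, or 12.1% (0.12055 before rounding)

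The upper bound on active participants not started is E[max(0, 30 − T)]. T is the position of the second affected participant, with P(T = t) = (t−1)p²(1−p)^(t−2). The bound assumes that the pause becomes permanent and that events are known at once.

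- p = 1%: 0.36
- p = 2%: 1.25
- If one or two more active participants start before the event is known: 0.32 or 0.29 at 1%, and 1.13 or 1.03 at 2%

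Multiplying the bound by p gives the seizures averted: at most 0.36 × 0.01 = 0.004 and 1.25 × 0.02 = 0.025.

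A first-event trigger would fire with probability 1 − (1−p)^30, which is 26.0% at 1% and 45.5% at 2%. If those rates were purely background post-stroke seizures, every pause under either trigger would be a false alarm.

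**The case against.** The strongest reply is that the synopsis line is a list of laboratory safety tests and was never meant to be the whole safety assessment. Section 5 has its own heading, and the definition in 5.1 plainly covers a seizure. Criterion 1 in section 3.4 could withdraw an affected participant. Section 3.6 reduces the risk beforehand, and section 6.1 allows urgent action. In one inpatient department, with one week of stimulation, staff would probably notice a seizure and could act on it.

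Much of this stands. A reader might infer that the protocol would leave seizures unrecorded, or that it assesses safety with no regard to them. The documents do not support that, because 5.1 brings seizures into scope. What does not stand is that scope amounts to process: a definition does not say who is told, when, or who reviews, and the other provisions either prevent events or act on one person.

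A reader might also infer that a trial-level pause rule is required. The documents do not support this either. They give no event rate, the threshold is a judgement, and step 5 shows almost no benefit at the assumed rates.

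It can also be said that tabulating events by arm is commonly left to the statistical analysis plan. That is fair for table layout. It does not cover which safety measures the protocol lists, or the reporting route.

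**Conclusion.** The point holds in a limited form. The listed safety indicators cannot register the harm that section 4.1 names, and no section states a reporting or review step for a seizure or an SAE. This is more than missing detail, because a safety conclusion that followed the stated list would omit that harm.

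It is an inexpensive improvement rather than a flaw that invalidates the trial. Its size cannot be stated from the documents, which give no seizure rate. The figures of 3.6% to 12.1% of trials, and about one participant spared at most, rest on assumed rates of 1% to 2% and concern only the optional pause. The case rests on recording and reporting the named risk and on protecting the participant who has a seizure, not on those figures.

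**What to change.** Amend the protocol in three places.

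1. **Safety indicators (synopsis, repeated in 3.8).** Add seizures and stimulation-related SAEs, by arm, from the first session to the 2-week follow-up. Counting by arm does not disturb the stated blind, which in section 3.7 covers participants.
2. **Section 5.** State that each such event is reported within a set time, for example 24 hours, to the Quality Control member and to the Ethics Committee, which review it.
3. **Section 3.4 or 4.1.** State that any participant who has a seizure receives no further stimulation.

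Optionally, allocation could pause for Ethics Committee review after a stated number of active-arm seizures, with the control-arm count supplied so that background seizures can be weighed. If this is adopted, the protocol should call the threshold a judgement and say that the count involves no look at efficacy data.

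The cost is a few sentences and a small reporting burden, using roles already named and with no extra participants. The optional pause adds the chance of a false alarm shown in step 5.
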